4.2 Tolerance

Side effects will be described by descriptive statistics and analyzed by T-test.

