1.1 Background

Cutaneous leishmaniasis (CL) is endemic in the New World from approximately the US-Mexican border through Central America and the Northern part of South America down to the level of Rio de Janeiro.

The cure rate for New World CL is only approximately 70% for all recognized therapies. For systemic therapy with the classic agent pentavalent antimony, recent cure rates of New World CL are 50% to 75% [1-5]. For the new oral agent miltefosine in 3 of these studies, the cure rate was 57-75% [2-4]. CL can also be treated locally. For intralesional (IL) antimony, cure rates are reported as 56-75% for Iranian CL [6-7], 80-83% for *L braziliensis* in Brazil [8-9], and most recently 70% for *L braziliensis* in Bolivia when the concomitant placebo cure rate was 18% [10].

A novel approach was to evaluate intralesional pentamidine for Bolivian CL. The rationale for IL pentamidine is that little drug is administered via intralesional injection, thus the toxicity of systemic pentamidine would be unlikely to be seen. For Bolivian CL, 3-injections of IL Pentamidine over 5 days cured 72% of patients whereas 3-injections of IL antimony over 5 days cured 57% [manuscript submitted]. Adverse effects were local irritation and injection site pain: IL pentamidine (30 patients)—mild (4 patients), moderate (3); IL antimony (60 patients)—mild (25 patients), moderate (4). No pentamidine patient experienced the side effects of systemic pentamidine administration: sterile abscess, hypotension, or hypoglycemia. We concluded that IL pentamidine is an attractive alternative to standard intralesional antimony for Bolivian *Leishmania braziliensis* on the basis of efficacy, the threat of antimony-resistant parasites, tolerance, and patient convenience of 3 visits over 5 days.

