1.2 Rationale

Although patients can be treated with one of these agent with the anticipation of an approximately 70% cure rate, and failures of the first treatment could then be treated with another agent, an initial cure rate > 70% would be desirable.

We propose to evaluate oral miltefosine plus intralesional pentamidine for Bolivian CL. Efficacy should be additive, since the postulated mechanisms of the drugs is different. The structure of miltefosine is similar to that of phosphatidylcholine, and may interfere with phosphatidylcholine biosynthesis or function[11]. In contrast, it is thought that pentamidine interferes with polyamine biosynthesis [12]. The advantage of the combination of oral miltefosine and IL pentamidine vs other possible drug combinations is that the systemic partner is oral rather than parenteral, and that the intralesional partner is the most active of the IL agents that we have found in Bolivia. The combination should be well tolerated, since the local side effects of pentamidine would not interact with the systemic gastrointestinal side effects of miltefosine. Finally, this combination would be

convenient, since intralesional injections of pentamidine would occur on days 1, 3, and 5 of the standard 28-day miltefosine treatment course when patients are already under medical care.

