2.0 Study Aims and design

2.1 Aim:

The primary purpose of this study is to evaluate the cure rate of a standard course of oral miltefosine in combination with intralesional pentamidine for single lesions predominately due to *L braziliensis* in Bolivia.

A secondary purpose is to determine the tolerance of this regimen.

2.2 Design:

Open label evaluation of miltefosine (28 days) plus intralesional pentamidine (days 1, 3, 5).

After treatment, all patients will be followed for 1, 3, and 6 months.

The initial number of patients will be 30.

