3.5 Adverse events recording

Re Miltefosine: Adverse events especially gastrointestinal will be recorded.

Re IL pentamidine: Patients will be evaluated for local side effects (pain, itching, irritation (erythema/edema), vesicles/bullae, sterile abscesses) and the possibility of bacterial superinfection both local and disseminated to the draining lymph nodes on each day that therapy is applied. Any other subjective complaint spontaneously referred by the patient will be registered and evaluated.

In addition, pentamidine patients will be evaluated for hypoglycemia.

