3.6 Procedural Timetable

Action	Day 0	Day 1	Day28	1 M	3 M	6M
Consent	X					
Hx /PE	X		X	X	X	X
Parasitology (aspirate:smear/cult)	X					
Evaluate lesion	X	X	X	X	X	X
Treatment						
Oral Miltefosine			day 1 to day 28			
IL pentamidine			days 1, 3, 5			
Adverse events (esp. GI)	X	day 1	to day 28			
Blood Glucose	X	weeks 2	and 4			
AST	X	weeks 2	and 4			
Creatinine	X	weeks 2	and 4			

“Day 0” includes the screening period.

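### Protocol 4.2 applies a t-test to side effects in a single-arm trial that records them as events, so the test has nothing to compare and does not suit the data

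*Protocol*

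**What the plan says.** Section 4.2 gives the whole tolerance analysis in one sentence: "Side effects will be described by descriptive statistics and analyzed by T-test". It names no variable, comparison group, reference value or form of the test.

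The design in Section 2.2 is a single regimen: "Open label evaluation of miltefosine (28 days) plus intralesional pentamidine (days 1, 3, 5"). The initial sample is 30 patients, and Section 2.1 makes tolerance of this regimen a secondary purpose.

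Section 3.5 sets out what is recorded. For miltefosine it is adverse events, chiefly gastrointestinal. For the intralesional drug: "Patients will be evaluated for local side effects (pain, itching, irritation (erythema/edema), vesicles/bullae, sterile abscesses"), together with bacterial superinfection and any complaint the patient volunteers. It adds: "In addition, pentamidine patients will be evaluated for hypoglycemia". The timetable in Section 3.6 schedules "Blood Glucose", AST and creatinine at Day 0 and at weeks 2 and 4.

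The protocol reports its own earlier tolerance data as patient counts by severity, in Section 1.1: "IL pentamidine (30 patients)—mild (4 patients), moderate (3").

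**The concern.** A t-test compares a mean with another mean or with a stated value. This trial has one arm, so there is no between-group comparison, and the protocol gives no reference value for a one-sample test. Most of what 3.5 collects is whether an event occurred, for which the natural summary is the proportion of patients affected and how precisely it is known.

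The aim of determining the tolerance of one regimen is descriptive. A p-value from a t-test would not tell the reader how often a side effect occurs, or how high the true rate could be when none is seen. The second question matters here. Section 1.1 reports of the earlier 30 patients: "No pentamidine patient experienced the side effects of systemic pentamidine administration: sterile abscess, hypotension, or hypoglycemia". The method should therefore cope with zero or near-zero counts as well as with the commoner local and gastrointestinal effects that Section 1.2 anticipates ("the local side effects of pentamidine would not interact with the systemic gastrointestinal side effects of miltefosine").

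**Working it through.** The protocol gives no numerical figure for tolerance (no alpha, power, effect size or SD), so there is nothing to reproduce. The check has two parts.

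**1. Which form of t-test could be meant?**

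| Form | What it needs | What the protocol supplies |
|---|---|---|
| Two-sample | A second group | None (2.2: one open-label regimen) |
| One-sample | A null value | None (4.2, 3.5) |
| Paired | The same numeric measure at two times | Not for the listed side effects; available for glucose, AST and creatinine (3.6: Day 0, weeks 2 and 4) |

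Only the paired form on laboratory values can be computed. Section 4.2 refers to side effects in general and does not mention those values.

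**2. What would a t method do with yes/no data at n = 30?** This is illustration only, since 4.2 specifies no form of test and plans no interval. Inputs: n = 30 (Section 2.2); an example count of 7 of 30, the earlier 4 mild plus 3 moderate (Section 1.1), assuming these are different patients.

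The t interval is p ± t(0.975; 29) × √[p(1 − p)/29], with t(0.975; 29) = 2.045. The comparator is the exact (Clopper-Pearson) interval.

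- 7/30: p = 0.233; standard error = √(0.233 × 0.767/29) = 0.0785; half-width = 2.045 × 0.0785 = 0.161; interval 7.3% to 39.4%.
- 0/30: the standard error is 0, so the interval has zero width and a test statistic is undefined. The exact upper limit is 1 − 0.025^(1/30) = 11.6%.

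| Patients with event | t interval | Exact 95% interval |
|---|---|---|
| 0/30 | 0 to 0 | 0 to 11.6% |
| 1/30 | −3.5% to 10.2% | 0.1% to 17.2% |
| 3/30 | −1.4% to 21.4% | 2.1% to 26.5% |
| 7/30 | 7.3% to 39.4% | 9.9% to 42.3% |

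Coverage of the nominal 95% intervals, summing binomial probabilities over 0 to 30 events:

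| True rate | t interval | Exact interval |
|---|---|---|
| 5% | 78.5% | 98.4% |
| 10% | 95.6% | 99.2% |
| 4/30 (13%) | 91.9% | 97.3% |
| 7/30 (23%) | 93.1% | 97.0% |

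The shortfall at 5% comes almost wholly from samples with no event: the chance of seeing at least one event in 30 patients is 1 − 0.95^30 = 78.5%, and with none the t interval is the single point zero. From about 10% upwards the t interval is usable, if slightly short of nominal at some rates.

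**The case against.** The strongest reply is that the t-test may have been meant for the laboratory safety values. Glucose, AST and creatinine are measured before and during treatment, Section 4.1 covers only cure, and so 4.2 is the one visible analysis section these data could fall under. A paired t-test of change from Day 0 is legitimate in a single arm, and naming the variables is often left to a statistical analysis plan. This is a fair reading of intent, and it applies to all three measures. It does not rescue the sentence as written, which attaches the test to side effects without restriction. Nor does mean glucose change show how many patients became hypoglycemic.

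A second reply is that the coverage figures judge an interval the protocol never proposes. That stands: they show what would follow if a t method were put on event data, and are not a measured fault of the plan.

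A third is that 3.5 lists what is evaluated and not how it is coded, and the earlier effects were graded mild or moderate, so a scale may be used. Also fair: the accurate statement is that no scale is stated. A severity grade would still leave the test without a comparison.

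Finally, no decision rests on the clause. That is correct and sets the severity. Section 3.9 plans a look at both cure and tolerance after 30 patients, but makes further enrollment conditional on cure rate only.

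**Conclusion.** The concern holds, as a minor one. The t-test clause in 4.2 does not fit a one-arm design with side effects recorded mainly as events, and this is an error in what the protocol states, not a detail left for later. The descriptive half of the sentence is valid and already serves the tolerance aim.

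For commoner side effects the fault is that the test answers no stated question. A numerical problem arises only for rare events, and only on the assumption that a one-sample t method would be applied to yes/no data from 30 patients. The use of 7/30 as an example further assumes that the mild and moderate cases are distinct patients. The main conclusion needs neither assumption: it follows from the design in 2.2 and the data in 3.5.

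**What to change.** Delete the t-test clause from 4.2. A suitable replacement for the section is:

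> The number and percentage of treated patients with each recorded side effect (by severity where recorded) will be reported with exact (Clopper-Pearson) 95% confidence intervals.

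The deletion corrects the error. The exact interval is a recommended addition; it is somewhat conservative (97% to 99% coverage in the cases above), but it gives a usable upper limit when no event is seen.

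If the t-test was meant for laboratory change, say so: name glucose, AST and creatinine, and the Day 0 to week 2 and Day 0 to week 4 comparisons already scheduled in 3.6, as a paired analysis separate from the side-effect counts.

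The cost is one sentence. No new data, visits or grading scale are needed, and no analysis is added unless laboratory change was intended.

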5.4 Data handling

[name] will devise CRFs, and check CRF data vs source data. Given the relatively low numbers of patients and relatively small numbers of data points, each entry in the CRF can be checked against the source data (2-person method).

5.5 Ethical review

The protocol will be approved by the responsible ethical committee as an extension of the IL pentostam/ IL pentamidine protocol.

The protocol will be listed on www.ClinicalTrials.Gov.

